6.1.2 Duration of therapy

Subjects may continue to receive acalabrutinib until meet the discontinuation criteria (Section 7.1). Safety follow-up assessments will be conducted at 30 days (+7 days) post last dose of therapy.

Subjects who discontinue study therapy due to reasons other than disease progression will continue on study for post-treatment disease follow up and subjects who have disease progression will be followed for survival (see Section 7.1.2) unless they withdraw consent or loss to follow up.

6.2 Preparation/handling/storage/accountability

The investigator or designee must confirm appropriate temperature conditions have been maintained during transit for all study treatment received and any discrepancies are reported and resolved before use of the study treatment.

Only subjects enrolled in the study may receive study treatment and only authorized site staff may supply or administer study treatment. All study treatments must be stored in a secure, environmentally controlled, and monitored (manual or automated) area in accordance with the labelled storage conditions with access limited to the investigator and authorized site staff.

The investigator, institution, or the head of the medical institution (where applicable) is responsible for study treatment accountability, reconciliation, and record maintenance (i.e., receipt, reconciliation, and final disposition records).

The unused study treatment will be returned to AstraZeneca for disposition.

6.3 Measures to minimize bias: randomization and blinding

There will be no randomization scheme in this study. All subjects across Phase 1 and Phase 2 will be assigned to receive acalabrutinib. This is an open-label study, methods for ensuring blinding is not applicable.

6.4 Treatment compliance

For acalabrutinib taken in the clinic, subjects should take the dose from the drug dispensed to them for that particular time period. All other study treatments will be taken at home. Subjects will receive a drug diary to record the specific time each dose was taken and to record reasons for any missed doses.

Subject compliance will be assessed at each study visit. The subject will be instructed to bring the diary and any remaining capsules to the clinic at their next visit. The study staff will review the diary and ask the subject if all of the capsules were administered. Any remaining or returned capsules will be counted and recorded in accountability records as described in Section 6.2. Returned capsules must not be redispensed to another subject.

The investigational product should only be used as directed in this protocol. Details of treatment with investigational product including: change from the dosing schedule, dose interruptions, dose reductions, dose discontinuations should be recorded in eCRF.

The investigational product will not be distributed to the study site until the contract is concluded between the study site and AstraZeneca. The investigator or designee is responsible for managing the IMP from receipt by the study site until the return of all unused IMP to

AstraZeneca. The Investigator(s) is responsible for ensuring that the subject has returned all unused IMP.

6.5 Concomitant therapy

Any medication or vaccine including over-the-counter or prescription medicines, vitamins, and/or herbal medication that the subject is receiving at the time of 4 weeks prior to starting study treatment and all concomitant treatments during the study must be recorded in the Electronic Case Report Form (eCRF) along with:

- Reason for use (Indication)
- Dates of administration including start and end dates
- Dosage information including dose, frequency and route

6.5.1 Permitted concomitant therapy

- Permitted concomitant therapy is acceptable during study treatment. Antiemetics are permitted if clinically indicated. Standard supportive care medications are permitted as per institutional standards. Use of hematopoietic growth factors is permitted per Consensus of Chinese Experts ([Version 2015](#)). (Primary prophylactic use of myeloid growth factors (e.g., granulocyte colony-stimulating factor [G-CSF]) is not allowed according to the guideline.)
- For subjects considered at risk for tumor lysis syndrome: Administer appropriate hydration and allopurinol or rasburicase per institutional standards before initiating treatment.
- Prophylaxis for bacterial/viral/fungal is allowed per institutional standards.
- During study participation, subjects may receive systemic or enteric corticosteroids at any required dosage as needed for treatment-emergent comorbid conditions such as treatment emergent colitis or pneumonitis.

6.5.2 Prohibited concomitant therapy

Any concurrent chemotherapy (e.g., bendamustine, cyclophosphamide, pentostatin, or fludarabine), anticancer immunotherapy (e.g., rituximab, obinutuzumab, alemtuzumab, or ofatumumab), corticosteroids (at dosages equivalent to prednisone >20 mg/day), kinase inhibitors (e.g., ibrutinib, zanubrutinib and idelalisib), bone marrow transplant, experimental therapy, and radiotherapy are prohibited.

Warfarin or equivalent vitamin K antagonists (e.g., phenprocoumon) are prohibited. Any herbal medication is prohibited from Cycle 0 Day 1 to Cycle 1 Day 8 (intensive PK sampling period) in Phase 1 portion. Administration of herbal medication during other treatment period is not recommended, unless it is prescribed by the investigator for treatment of specific clinical events. At study entry, subjects may be using topical or inhaled corticosteroids or

steroids (≤ 20 mg of prednisone or equivalent per day) as therapy for comorbid conditions but use of corticosteroids as therapy of the lymphoid cancer is not permitted.

Immunization with a live virus vaccine is prohibited within 28 days before study treatment and during study treatment.

The effect of agents that reduce gastric acidity (antacids or proton pump inhibitors) on acalabrutinib absorption was evaluated in a healthy volunteer study (ACE-HV-004). Results from this study indicate that subjects should avoid the use of calcium carbonate containing drugs or supplements for a period of at least 2 hours before and at least 2 hours after taking acalabrutinib. Use of omeprazole or esomeprazole or any other proton pump inhibitors while taking acalabrutinib is strongly not recommended due to a potential decrease in study drug exposure. If treatment with an H2-receptor antagonist is required, the H2-receptor antagonist should be taken approximately 2 hours after an acalabrutinib dose.

At the systemic exposure levels expected in this study, acalabrutinib inhibition of CYP metabolism is not anticipated. However, concomitant administration of acalabrutinib with a strong CYP3A inhibitor increased exposure by approximately 5-fold. Conversely concomitant administration of a strong inducer of CYP3A has the potential to decrease exposure of acalabrutinib and could reduce the efficacy of the study interventions. Consequently, the concomitant use of strong inhibitors/inducers of CYP3A (e.g. clarithromycin, itraconazole, carbamazepine and St John's wort) should be avoided when possible. Refer to [Table 6](#) for Instruction for Coadministration of Drugs with Acalabrutinib Coadministered Drug.

Table 6 Instructions for Coadministration of Drugs with Acalabrutinib Coadministered Drug

Instructions for Coadministration of Drugs with Acalabrutinib Coadministered Drug	Acalabrutinib
Strong CYP3A inhibitor	Avoid concomitant use with acalabrutinib. If the inhibitor will be used short-term (such as anti-infectives for up to 7 days), interrupt acalabrutinib.
Moderate CYP3A inhibitor	No dose adjustment. Monitor patients closely for adverse reactions if taking moderate CYP3A inhibitors.
Strong CYP3A inducer	Avoid concomitant use. If a subject requires treatment with a strong CYP3A inducer, increase the acalabrutinib dose to 200 mg BID during concomitant administration with the strong inducer and return to recommended dose of 100 mg BID after stopping the strong CYP3A inducer.

Instructions for Coadministration of Drugs with Acalabrutinib Coadministered Drug	Acalabrutinib
Moderate CYP3A inducer	No change
P-gp inhibitor	No change
BCRP inhibitor	No change
Narrow therapeutic index P-gp substrate	No change
Bile acid sequestrants	No change
Statin (OATP substrate)	No change
Proton pump inhibitors	Avoid concomitant use.
H2-receptor antagonists	Take acalabrutinib 2 hours before taking a H2-receptor antagonist.
Antacids	Separate dosing by at least 2 hours.

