2.2.3.3 Clinical Pharmacology

Acalabrutinib has a short PK half-life with a long-lasting pharmacodynamic effect due to covalent binding to BTK.

Acalabrutinib is highly permeable, and is rapidly and nearly completely absorbed after oral dosing over the studied dose range up to 400 mg. Acalabrutinib solubility is pH-dependent across the physiologic pH range; however, solubility is high in acidic conditions up to pH 4 (e.g., normal gastric pH). PK properties of acalabrutinib in healthy adult subjects were evaluated after oral administration of 2 daily divided doses of 2.5 to 50 mg and a single dose

of 100 mg. Acalabrutinib plasma t_{max} values were between 0.5 and 1.0 hour for all dose cohorts, and were independent of dose level. Mean half-life values ranged from 0.97 hours to 2.1 hours.

Acalabrutinib has an absolute oral bioavailability of 25% (range 20% to 30%) and can be taken with or without food. Acalabrutinib does not accumulate in plasma upon repeat-dose administration. Based on population PK analysis, acalabrutinib PK was linear over the 75 to 250 mg dose range. At a dose of 100 mg BID, exposure and an elimination half-life of approximately 1 hour were relatively comparable across most individuals in healthy subject and patient studies. Variability in exposure to acalabrutinib is mainly due to a combination of pH-dependent dissolution and absorption and predominantly CYP3A-mediated metabolism.

Acalabrutinib is extensively and nearly completely metabolized by three major pathways. The most abundant circulating metabolite in human was ACP-5862 (denoted M27) which was formed by CYP3A and also circulated in nonclinical species. A PBPK model incorporating acalabrutinib and active metabolite ACP-5862 (M27) BTK binding kinetics, plasma protein binding and clinical PK indicated that ACP-5862 may contribute to BTK target coverage.

Therapeutic plasma acalabrutinib concentrations after a 100-mg dose or supratherapeutic plasma acalabrutinib concentrations after a 400-mg dose in healthy subjects did not prolong the QTc interval in a thorough QT study.

The 100 mg BID dose and schedule was selected for most oncologic indications because it results in continuous near-saturation BTK target coverage with the least inter-subject variability and an acceptable safety profile.

Further details can be found in the latest version of the investigator brochure.

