2.2.3.4 Drug-drug Interaction Potential

At the systemic exposure levels expected in this study, acalabrutinib inhibition of CYP metabolism is not anticipated. However, acalabrutinib is metabolized by CYP3A.

Concomitant administration of acalabrutinib with a strong CYP3A inhibitor, itraconazole increased exposure by approximately 5-fold. Additionally, concomitant administration of acalabrutinib with moderate CYP3A inhibitors, fluconazole and isavuconazole, increased exposure by approximately ≤ 2 -fold. Conversely, concomitant administration of acalabrutinib with a strong CYP3A inducer, rifampin decreases acalabrutinib exposure by 77%.

Consequently, the concomitant use of strong inhibitors/inducers of CYP3A should be avoided when possible. Alternatively, if the strong inhibitor will be used short-term (such as anti-infectives for up to seven days), interrupt acalabrutinib. When acalabrutinib is administered with moderate CYP3A inhibitors, no dose adjustment is needed but monitor patients closely for adverse reactions. If a strong CYP3A inducer cannot be avoided, increase the acalabrutinib dose to 200 mg twice daily. See Appendix E for a list of strong CYP3A inhibitors/inducers.

The effect of agents that reduce gastric acidity (antacids or proton-pump inhibitors) on acalabrutinib absorption was evaluated in a healthy volunteer study (ACE-HV-004). Results from this study indicate that subjects should avoid the use of calcium carbonate-containing drugs or supplements for a period of 2 hours before and at least 2 hours after taking acalabrutinib. Use of omeprazole, esomeprazole, lansoprazole or any other proton-pump inhibitors while taking acalabrutinib is not recommended due to a potential decrease in study drug exposure. However, the decision to treat with proton-pump inhibitors during the study is at the investigator's discretion, with an understanding of the potential benefit to the subject's gastrointestinal condition and a potential risk of decreased exposure to acalabrutinib.

If treatment with an H2-receptor antagonist is required, the H2-receptor antagonist should be taken approximately 2 hours after an acalabrutinib dose.

For more detailed information on drug-drug interaction potential for acalabrutinib, refer to the Investigator Brochure.

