4.3 Justification for dose

The recommended dose of acalabrutinib is 100 mg BID based on the following data:

In the Phase 1/2 study in subjects with CLL/SLL (ACE-CL-001), subjects have received acalabrutinib at dosages from 100 mg QD to 400 mg QD or 100 mg to 200 mg BID. No dose-limiting toxicities (DLTs) were identified at dosages of \leq 400 mg once per day (QD) or 100 to 200 mg BID. With a median follow up of 15.5 months in evaluable subjects (n=128), the best overall response rate, including partial response and partial response with lymphocytosis (PR+L), was 96.9%.

Pharmacodynamics results from ACE-CL-001 suggest BTK resynthesis occurs in malignant B cells within 24 hours. While all dosages evaluated show full BTK occupancy 4 hours after dosing, the 100 mg BID cohort shows full target coverage over 24 hours (\geq 97% BTK occupancy at 4 and 24 hours). Based on pharmacokinetics/pharmacodynamics and efficacy results of the Phase 1/2 study, acalabrutinib 100 mg BID is selected as the recommended dose.

In a multicenter, open-label Phase 2 Study (ACE-LY-004) in subjects with R/R MCL, Acalabrutinib 100 mg BID monotherapy was generally well tolerated and resulted in a high ORR and CR rate, with responses that were durable and clinically meaningful. Please refer to Section 2.2.3.5.

In an ongoing Japanese Phase 1 study (D8220C00001), preliminary data from Part 1 (the dose-confirmation phase) showed acceptable safety and tolerability profiles. No DLTs was observed among the 6 evaluable subjects. No clinical relevant PK ethnic difference was observed between Japanese and Western subjects.

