- 23 Ongoing immunosuppressive therapy, including systemic (e.g., IV or oral) corticosteroids of underlying disease within 2 weeks before the first dose of study drug. Note: Subjects may use topical or inhaled corticosteroids or steroids (\leq 20 mg prednisone equivalent/day for \leq 2 weeks) as a therapy for comorbid conditions. During study participation, subjects may also receive systemic (e.g., IV or oral) corticosteroids as needed for treatment-emergent comorbid conditions.
- 24 Use of a strong inhibitor or inducer of CYP3A within 7 days before dose of study drug or expected requirement for use of a CYP3A inhibitor or inducer (including herbal medication known to modulate CYP3A4 enzyme activity) during the first 28 days of administration of study drugs.
- 25 Received a live virus vaccination within 28 days of first dose of study drug.
- 26 History of allergy or hypersensitivity to any component of the acalabrutinib formulation

Prior/concurrent clinical study experience

- 27 Concurrent participation in another therapeutic clinical trial.

Other exclusions

- 28 Breastfeeding or pregnant (breastfeeding is not allowed during treatment and until 2 days after the end of treatment. However, resumption of breastfeeding 2 days after the last dose is allowed.)

29 Judgment by the investigator that the subject should not participate in the study if the subject is unlikely to comply with study procedures, restrictions and requirements.

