6.6.2 Dose modification

The actions in Table 7 should be taken for the following toxicities (according to CTCAE criteria version 5.0 or higher):

- Grade 4 neutropenia (ANC $< 500/\mu\text{L}$) for > 7 days (Myeloid growth factors are permitted per Consensus of Chinese Experts ([Version 2015](#)) and use must be recorded on the eCRF).

- Grade 3 platelets decreases in the presence of clinically significant bleeding
- Grade 4 platelets decreases
- Grade 3 or 4 nausea, vomiting, or diarrhea, if persistent despite optimal antiemetic and/or anti-diarrheal therapy
- Any other Grade 4 toxicity or unmanageable Grade 3 toxicity.

If the toxicity resolves or reverts to \leq CTCAE grade 1 or baseline within 28 days of onset and the subject is showing clinical benefit, treatment with acalabrutinib may be restarted using the rules below for dose modifications (see [Table 7](#)). Whenever possible, any dose adjustment of acalabrutinib should be discussed between the investigator and the sponsor before implementation. The appropriate clinic staff should dispense the study drug for the new dose level and instruct the subject/caregiver about the change in dose level. Any changes to the dosing regimen must be recorded in the appropriate eCRF.

In case a dose reduction is necessary, the study intervention will be administered as follows.

Dose modification guidelines for study intervention-related toxicities are provided below. Appropriate and optimal treatment of the toxicity is assumed prior to considering dose modifications. Prior to discontinuation of study intervention due to toxicities, please consult with the study physician.

Table 7 Dose modifications for toxicity

Occurrence	Action
1 st -2 nd	Hold acalabrutinib until recovery to Grade \leq 1 or baseline; may restart at original one-day dose level (100 mg BID)
3 rd	For non-hematologic AEs, discontinue acalabrutinib. For thrombocytopenia with significant bleeding, discontinue acalabrutinib. For other hematologic AEs, upon recovery to Grade \leq 1 or baseline, restart at 100 mg QD.
4 th	For hematologic AEs, discontinue acalabrutinib.

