8.4.3 Overdose

For this study, any dose of acalabrutinib greater than the dose being studied will be considered an overdose. However, if acalabrutinib is administered with strong CYP3A inducers, the recommended dose is 200mg BID (Table 6). It is not considered as overdose in this situation. Avoid co-administration of strong CYP3A inducers with acalabrutinib.

For any subject experiencing an acalabrutinib overdose, observation for any symptomatic side effects should be instituted, and vital signs, biochemical and hematologic parameters, and ECGs should be followed closely (consistent with the protocol or more frequently, as needed). Appropriate supportive management to mitigate adverse effects should be initiated. If the overdose ingestion is recent and substantial, and if there are no medical contraindications, use of gastric lavage or induction of emesis may be considered.

Such overdoses should be recorded as follows:

- An overdose with associated AEs is recorded as the AE diagnosis/symptoms on the relevant AE modules in the CRF and on the Overdose CRF module.
- An overdose without associated symptoms is only reported on the Overdose CRF module

If an overdose on an IMP/study intervention occurs in the course of the study, then the investigator or other site personnel inform appropriate AstraZeneca representatives immediately, or **no later than 24 hours** of when they become aware of it.

The designated AstraZeneca representative works with the Investigator to ensure that all relevant information is provided to the AstraZeneca Patient Safety data entry site within one or 5 calendar days for overdoses associated with a SAE (see Section 8.3.2), and within 30 days for other overdoses

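### Table 6 gives 100 mg BID as the only dose after a strong CYP3A inducer stops and makes no exception for a subject already reduced to 100 mg QD under Table 7

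*Protocol*

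**What the plan says.** Protocol Section 6.5.2, Table 6, tells sites to avoid strong CYP3A inducers. If one is required, the dose becomes 200 mg BID for as long as the inducer is taken, and the subject is then to "return to recommended dose of 100 mg BID after stopping the strong CYP3A inducer". Section 4.3 fixes what recommended means: "The recommended dose of acalabrutinib is 100 mg BID".

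Section 6.6.2, Table 7, sets a lower level. At the third occurrence of a qualifying hematologic toxicity, other than low platelets with significant bleeding, the subject who recovers is to "restart at 100 mg QD". A fourth hematologic occurrence ends treatment.

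The inducer dose appears again in Section 8.4.3: "if acalabrutinib is administered with strong CYP3A inducers, the recommended dose is 200mg BID". That sentence makes no exception for a reduced subject, and neither does Section 2.2.3.4. On dose changes in general, Section 6.6.2 says: "Whenever possible, any dose adjustment of acalabrutinib should be discussed between the investigator and the sponsor before implementation".

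**The concern.** The protocol has two maintenance doses but only one post-inducer instruction, written as a number. For a subject on 100 mg QD, the verb in Table 6 points back to 100 mg/day and the number points to 200 mg/day. A site that follows the number restores the full daily dose in someone reduced for repeated hematologic toxicity, for a reason unrelated to that toxicity.

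Section 2.3.2.2 lists cytopenias as an important identified risk and sends the reader to Section 6.6.2 for dose guidance, so Table 7 is the protocol's control for that risk. Table 6, read literally, undoes it. What is at stake is the dosing of an individual subject. No endpoint, sample size or planned analysis is involved.

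**Working it through.** The plan states no figure to reproduce here. The check compares the two tables and then does daily-dose arithmetic.

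**Text**

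| Situation | Instruction | Daily total |
|---|---|---|
| Usual dose (Section 4.3) | 100 mg BID | 2 × 100 = 200 mg |
| Third qualifying hematologic event (Table 7) | 100 mg QD | 100 mg |
| During a strong inducer (Table 6) | 200 mg BID | 2 × 200 = 400 mg |
| After the inducer stops (Table 6) | 100 mg BID, no other dose named | 200 mg |

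Nothing in the current text says that a Table 7 reduction persists after inducer use. The version history records that a sentence barring a restart at the original dose was removed. Table 6 therefore breaches no ban on re-escalation, but no rule elsewhere overrides its number either.

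**Return step.** 200 / 100 = 2.0 times the Table 7 daily dose. This needs no pharmacokinetic assumption. Each intake stays at 100 mg, so the change is in daily exposure and not in the size of a single dose.

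**Change in exposure when the inducer stops.** Inputs:
- Exposure loss: Section 2.2.3.4 says "rifampin decreases acalabrutinib exposure by 77" percent.
- Linearity: Section 2.2.3.3 says "acalabrutinib PK was linear over the 75 to 250 mg dose range", which covers single doses of 100 and 200 mg.

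Uninduced-equivalent dose on the inducer = 400 × (1 − loss). Step on stopping = return dose / that equivalent.

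| Exposure loss | Equivalent on inducer | Return to BID | Return to QD |
|---|---|---|---|
| 77% (rifampin) | 400 × 0.23 = 92 mg/day | 200/92 = 2.17 | 100/92 = 1.09 |
| 70% (assumed) | 400 × 0.30 = 120 mg/day | 200/120 = 1.67 | 100/120 = 0.83 |
| 80% (assumed) | 400 × 0.20 = 80 mg/day | 200/80 = 2.50 | 100/80 = 1.25 |
| 50% (assumed, wide range) | 400 × 0.50 = 200 mg/day | 200/200 = 1.00 | 100/200 = 0.50 |
| 90% (assumed, wide range) | 400 × 0.10 = 40 mg/day | 200/40 = 5.00 | 100/40 = 2.50 |

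With a rifampin-like inducer, exposure on 200 mg BID is 92/100 = 0.92 of the reduced dose. A return to QD roughly keeps it there and a return to BID roughly doubles it. The figures are for parent drug only. The active metabolite, itself formed by CYP3A, is not modelled.

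**Frequency.** The documents give none. The subject must have three qualifying hematologic toxicities, recover and still benefit, and then need a strong inducer. The exclusion criteria bar "Use of a strong inhibitor or inducer of CYP3A within 7 days before dose of study drug", and also an expected need for CYP3A inhibitors or inducers in the first 28 days. Treatment continues until progression, so later use is possible, and Table 6 itself provides for it.

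**The case against.** The strongest reply is that the tables do not conflict. Table 7 sets a restart dose and does not cap later dosing. To return means to go back, so the Table 6 clause describes someone who was on 100 mg BID and simply does not address the reduced subject. That stands in part: this is an unaddressed corner case and not a direct contradiction. It does not settle the dose, because the verb is followed by an explicit number.

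A second reply is that other safeguards would catch the error. Hematology is repeated throughout treatment, safety concerns go promptly to the sponsor, treatment may stop for an adverse event posing substantial risk, and a safety review committee is in place. These make an unnoticed return to BID less likely. None names a return dose, and the sponsor discussion in Section 6.6.2 is required only when possible.

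A third reply is that harm has not been shown. The end point, 200 mg/day, is the standard study dose, and Section 4.3 reports no dose-limiting toxicities at up to 400 mg QD or 100 to 200 mg BID. The documents give no dose-response for hematologic toxicity. This stands: the added risk cannot be sized. The fourth-occurrence stopping rule applies equally on QD and adds nothing to the case.

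Finally, the version history ties the clause to the Investigator's Brochure, which may address reduced subjects. It is not available here, and a site dosing from the protocol would still meet the unqualified number.

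**Conclusion.** The concern holds as a low-severity point that should be corrected. Table 6 names one post-inducer dose and has no exception for a subject on 100 mg QD. The literal instruction doubles that subject's daily dose (2.0 times). When a rifampin-like inducer stops, exposure rises 2.17 times instead of 1.09 times.

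The doubling follows from the text alone. The exposure ratios rest on the 77% figure, linear pharmacokinetics and parent drug only. The rows for other inducers rest on assumed losses. The case is expected to be very rare among about 105 planned subjects (12 + 33 + 60), but that is a judgement from the conditions required, because no rate is given.

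**What to change.** In Table 6, change the return clause so that, once the strong inducer is stopped, the dose is 100 mg BID, or 100 mg QD if it was reduced under Table 7 before or during inducer use. Add a cross-reference to Table 7. If the sponsor does intend re-escalation to BID, the same line should say so.

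This point covers the return step only, and the edit leaves the 200 mg BID step as written. That step also has no instruction for a subject on QD, or for one reduced while on the inducer, and the sponsor may wish to settle it at the same time.

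The cost is one phrase and one cross-reference, by clarification letter or at the next amendment. Dosing of subjects not reduced under Table 7 does not change.
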